PROPOSAL SUMMARY

Host Organization: University Hospital Río Hortega

Project Title: Predicting overall survival in glioblastomas using radiomic features of intraoperative ultrasound. A proposal for the creation of an international database of brain tumor ultrasound images.

Type of study: Ambispective observational

Start date & Duration: 1/10/2021 – 30/03/2022

1. Lay Abstract

Predicting the survival of patients diagnosed with glioblastoma (GBM) is essential to guide surgical strategy and subsequent adjuvant therapies. Intraoperative ultrasound (ioUS) is a low-cost, versatile technique available in most neurosurgical departments. The images from ioUS contain biological information possibly correlated to the tumor's behavior, aggressiveness, and oncological outcomes. Today's advanced image processing techniques require a large amount of data. Therefore, we propose creating an international database aimed to share intraoperative ultrasound images of brain tumors. The acquired data must be processed to extract radiomic or texture characteristics from ioUS images. The rationale is that ultrasound images contain much more information than the human eye can process. Our main objective is to find a relationship between these imaging characteristics and overall survival (OS) in GBM. The predictive models elaborated from this imaging technique will complement those already based on other sources such as magnetic resonance imaging (MRI), genetic and molecular analysis, etc. Predicting survival using an intraoperative imaging technique affordable for most hospitals would greatly benefit the patients' management.

2. Scientific Summary

We plan to carry out a multicentre retrospective study of patients operated with GBM diagnosis between January 2018 and January 2020, in order to set the base for future prospective collection of patients. All cases with an ioUS study will be included. All patients must count with B-mode modality. After an pseudonymization process, the images will be uploaded to a private cloud server. Demographic, clinical, conventional radiological, and molecular variables (IDH, MGMT) will also be collected. OS will be defined as the time elapsed between the histopathological diagnosis and the patient's death. The acquired data must be processed to

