obtain a series of radiomic markers to perform the study. A pre-processing stage will be necessary (noise cleaning, despeckling, intensity normalization, filtering) to calculate radiomics measurements (histogram, volumetric, shape, texture, etc.). In the previous stage, a very high number of radiological features per subject will be calculated. Because the number of features is much higher than the data set, to avoid the curse of dimensionality, it will be necessary to reduce their number using feature selection and extraction techniques (standard in pattern recognition and radiomics) that allow choosing those characteristics (or transformations of them) that have greater discriminating power. A predictive model of survival will then be elaborated based on the features selected.

3. Project Details

3.1 Background and Scientific Rationale:

GBM are the most common primary brain neoplasm. The survival of these patients is approximately 15 months despite continuous efforts to find more effective treatments. ioUS is a low-cost, versatile imaging technique available in most neurosurgical departments. These images contain biological information with potential application in surgical practice in addition to being a handy technique for image-guided brain tumor surgery. Advanced modalities, such as contrast-enhanced ultrasound (CEUS), intraoperative ultrasound elastography (IOUS-E), and navigated three-dimensional (3D) ultrasound, currently make it possible to exploit the full potential of this imaging technique to achieve maximal safe tumor resections.

On the other hand, advanced medical image analysis allows the development of predictive survival models using radiomic features. Even though ioUS image quality and resolution could be considered inferior compared to other imaging techniques, such as MRI, there is growing evidence that the ultrasound images contain biological information that can be set as a base to create models that allow classification tasks such as benignity versus malignancy. The ultrasound's capacity as a prognostic marker in response to adjuvant treatments in breast pathology has recently been evaluated. One possible explanation may lie in the fact that echogenicity in the B-mode could be associated with cellularity, which, on the other hand, is related to tumor aggressiveness.

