3.2 Hypotheses

Intraoperative ultrasound images in B-mode harbour tumor texture features correlated with overall survival in glioblastomas.

3.4 Objectives:

- To determine the relationship between the radiomic features of intraoperative ultrasound B-mode and overall survival in glioblastomas.
- Develop a predictive survival model using the texture features with the highest discriminatory power.
- Validate the model against an external dataset and compare it with currently available predictive models.
- Build a data set that allows exploring various image harmonization techniques that allow the reproducibility of our predictions.
- Establish an international cooperation network (**BraTioUS-DB**) whose objective will be to interchange ultrasound images and clinical data of patients operated on for a brain tumor prospectively from its creation and start-up.

4. Research Plan:

4.1 Study sample:

The cases that meet the inclusion criteria mentioned in the following section will be collected retrospectively to carry out the project's first phase. From January 2018 to January 2020, it is

estimated that each center can contribute with a minimum of 20 cases. Therefore, the total sample size for this phase of the study will be approximately 120 patients.

4.2 Selection of patients:

The inclusion criteria will be:

- Adult patients operated between January 2018 and January 2020 with a pathological diagnosis of WHO grade IV astrocytoma (Glioblastoma).
- Intraoperative ultrasound study that includes B-mode images

The exclusion criteria will be:

- Other histopathological diagnoses. Even though the international database will be established in such a way that other tumor types can be included prospectively.
- Artifacts in ultrasound images that make their analysis impossible
- Stereotactic biopsies.

4.3 Data collection (retrospective phase):

Each center will collect the details of the intraoperative acquisition technique of the ultrasound images. These data should include:

- Manufacturer of the ultrasound equipment,
- Type of probe: linear, curve.
- Footprint size
- Frequency range
- Modality. Essential B-mode, other modes optional.
- Acquisition before or after dural opening.
- Co-registered magnetic resonance images when possible (navigated ultrasound).
- Number of explorers who perform the ultrasound study.

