The transfer of data about human beings to the repository will only be considered when: informed consents, ethical approval and, where applicable, approval of local data protection authorities cover the purpose for which the data is intended to be used. Since this study involves patients diagnosed with glioblastomas, the cases have perished at the time of data collection. Therefore, the exemption of informed consent will be requested for the retrospective phase of the study (see Annex). On the contrary, for the prospective collection of cases, the informed consent model will be used (see Annex). All data to be transferred to the repository will be pseudonymized. The data owner/data provider will be responsible for the pseudonymization process and ensure that identifiable variables are not transferred to the repository.

7. Communication Plan for Dissemination:

This project's results will be disseminated through its publication in scientific journals and international conferences focused on neuroimaging, ultrasound, neurosurgery, and neuro-oncology.

8. Outputs: Impact, potential beneficiaries and added value:

The research work, aligned with one of the items of the Horizon 2020 program (Health, Demographic Change and Wellbeing) in addition to two of the United Nations Sustainable Development Goals (Health and well-being, 3; Industry, Innovation and Infrastructure, 9), has a great potential for impact, both at a scientific-technical level and a socio-economic level.

Concerning the scientific-technical, it is considered that the development of models for pre-processing, advanced analysis of ultrasound images that apply to commercial scanners and that, in turn, derive in descriptors that generate a large amount of useful information about the macro and microstructural properties of brain tumors, will lead to an increase in the use of advanced ultrasound techniques in clinical practice and will generate an increase in scientific research projects focused on these imaging technique. Furthermore, such models' implementation will substantially improve radiological care (diagnosis, early detection and treatment).

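### The consent exemption assumes every retrospective patient is dead, but the protocol's own dates and 15-month survival imply about 3 to 28 of 120 still alive

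*Protocol*

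**What the plan says.** Section 6 (Ethics) asserts, on the strength of the diagnosis alone: "Since this study involves patients diagnosed with glioblastomas, the cases have perished at the time of data collection". The next sentence draws the consequence: "Therefore, the exemption of informed consent will be requested for the retrospective phase of the study (see Annex". The visible text gives no other ground.

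The rest of the protocol describes a cohort that is not restricted to the dead:

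- Section 2 (Scientific Summary): "All cases with an ioUS study will be included".
- Section 4.2 (Selection of patients): "Adult patients operated between January 2018 and January 2020 with a pathological diagnosis of WHO grade IV astrocytoma (Glioblastoma". The only other inclusion criterion is a B-mode study. The exclusions are other histology, unusable images and stereotactic biopsy; being alive is not among them.
- Proposal summary: "Start date & Duration: 1/10/2021 – 30/03/2022".
- Section 3.1 (Background): "The survival of these patients is approximately 15 months despite continuous efforts to find more effective treatments". Whether this is a median or a mean is not stated.
- Section 4.1 (Study sample): "Therefore, the total sample size for this phase of the study will be approximately 120 patients".

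The endpoint is defined in Section 2: "OS will be defined as the time elapsed between the histopathological diagnosis and the patient's death". The protocol does not mention patients alive at data collection, and the patient-level list in Section 4.3 contains neither vital status nor a date of last contact.

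**The concern.** The last patients could have been operated on only about 20 months before the project starts. With survival of about 15 months, some of them, and some operated on earlier, should still be alive. Two things follow.

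First, the ethics committees of six centres would be asked to waive consent on a factual ground that the eligibility criteria do not secure and that is probably wrong for some patients.

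Second, the endpoint definition fits the same premise: it gives a value only to patients who have died. If the premise is carried into the analysis and living patients are left out, inclusion depends on the outcome. The longest survivors are lost, observed survival is biased short, and the association between features and survival, which is the main objective, is weakened.

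**Working it through.** **Sample size.** The host plus five listed collaborators make 6 centres. At 20 cases each, 6 × 20 = 120, which reproduces the stated figure.

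**Potential follow-up.** Surgery runs from 1 January 2018 to 1 or 31 January 2020 (the protocol gives only the month). Collection is assumed to fall within the project dates.

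- On 1 October 2021: 20.0 or 21.0 months (last patient) to 45.0 months (first patient).
- On 30 March 2022: 25.9 or 26.9 to 50.9 months.

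**Expected number alive.** Assumptions: 15 months is a median, surgery dates are uniform over the window, diagnosis is at surgery, and n = 120. Survival is S(t) = exp(−ln 2 × (t/15)^k). The alive fraction p is the average of S(t) over follow-up from a to b months, and the chance that all have died is (1 − p)^120.

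For k = 1 there is a closed form, p = [exp(−λa) − exp(−λb)] / [λ(b − a)], with λ = ln 2/15 = 0.0462. For a = 21.0 and b = 45.0: p = (0.379 − 0.125)/1.109 = 0.229, and 120 × 0.229 = 27.5.

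| Survival shape | Date | p | Alive of 120 | Chance all dead |
|---|---|---|---|---|
| Exponential (k = 1) | 1 Oct 2021 | 0.229–0.235 | 27–28 | below 0.02% |
| Exponential (k = 1) | 30 Mar 2022 | 0.174–0.179 | 21–22 | below 0.02% |
| Weibull k = 1.5 | 1 Oct 2021 | 0.127–0.135 | 15–16 | below 0.02% |
| Weibull k = 1.5 | 30 Mar 2022 | 0.070–0.075 | 8–9 | below 0.02% |
| Weibull k = 2 | 1 Oct 2021 | 0.066–0.074 | 8–9 | at most 0.03% |
| Weibull k = 2 | 30 Mar 2022 | 0.023–0.027 | about 3 | 4–6% |

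**Sensitivity.** If 15 months is a mean, the Weibull scale is 15/Γ(1 + 1/k). Then p is 0.015 to 0.128, or about 2 to 15 alive. The chance that all are dead is at most 0.3% at the start and 16% at the end. Log-normal and log-logistic curves with median 15 give about 8 to 30 alive.

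**Median survival if living patients are dropped** (true median 15 months; start to end of project):

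- Exponential: 10.4 to 11.5 months.
- Weibull k = 1.5: 13.1 to 14.0 months.
- Weibull k = 2: 14.2 to 14.8 months.

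**Effect on an association.** This is an illustration, not an analysis the protocol specifies: a Cox model, n = 120, one standard normal feature, marginal median 15 months, two-sided 5% test. There were 4,000 replicates for a hazard ratio (HR) of 1.5 per SD and 2,000 for 1.3.

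| True HR | Shape | Dropped, project start: HR (power) | Dropped, project end: HR (power) |
|---|---|---|---|
| 1.5 | k = 1 | 1.21 (36%) | 1.24 (47%) |
| 1.5 | k = 1.5 | 1.30 (66%) | 1.34 (78%) |
| 1.5 | k = 2 | 1.37 (85%) | 1.42 (93%) |
| 1.3 | k = 1 | 1.13 (18%) | 1.15 (24%) |
| 1.3 | k = 1.5 | 1.18 (33%) | 1.21 (45%) |
| 1.3 | k = 2 | 1.23 (54%) | 1.26 (62%) |

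With survivors censored instead, the estimates are 1.51 to 1.52 (power 96 to 98%) and 1.30 to 1.31 (power 68 to 78%).

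**The case against.** The strongest reply is that time from diagnosis to death is an ordinary endpoint definition, and that censoring rules and the choice of survival model usually belong in a statistical analysis plan, which is not shown here. No passage says living patients are dropped; Section 2 says the opposite. This stands: the bias is conditional, and the hazard ratios and power figures illustrate a mechanism under assumed inputs. The size also varies widely, from a shift in the median of 0.2 months to 4.6 months.

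On consent, the Annex that Section 6 cites is not available and may give further grounds. Section 6 also makes transfer of data conditional on consents, ethical approval and, where applicable, data protection approval, and the committees still decide. That limits what can be said about the request itself. It does not make the sentence in Section 6 true, and a statistical analysis plan cannot correct it.

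Finally, the dates are project dates rather than a stated collection window, and 15 months may be a mean. In the combination most favourable to the protocol (mean 15 months, Weibull shape 2, end of project), there is up to a 16% chance that all 120 have died. The premise is therefore very probably false rather than certainly so. Even there about 2 survivors are expected, and every other combination makes survivors more likely.

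**Conclusion.** The concern holds. Section 6 states as fact that the retrospective patients are dead and rests the consent exemption on it, while Sections 2 and 4.2 admit living patients and the protocol's dates make some very likely. The expected number alive is about 3 to 28 of 120 with 15 months as a median, and about 2 to 15 with it as a mean. The range reflects the survival shape and the calendar date as well as that reading, and it assumes uniform accrual.

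The contradiction and its use as the ground for the exemption do not depend on any document not shown, and must be corrected. The effect on overall survival depends on living patients being left out. If they are, its direction is certain (shorter survival, weaker associations) and its size runs from slight to severe.

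**What to change.** - Delete the statement in Section 6 that the patients have died, and reconcile that section with Sections 2 and 4.2.
- Restate the exemption request so that it does not depend on all patients being dead, and put the handling of living patients to the ethics committees.
- Add to Section 4.3, for every retrospective patient, vital status and the date of death or last contact.
- Define overall survival as time from histopathological diagnosis to death from any cause, with living patients censored at last contact. State that the prediction model and its performance measure must allow for censoring; the details can go in the statistical analysis plan.

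The cost is protocol wording, two data fields per patient and a corrected request. The committees may set extra steps for living patients. No additional patients are needed.
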